3.2 Recruitment, screening and informed consent procedure

Eligible patients will be screened by the participating gastroenterologist, endocrinologist or visceral surgeon. Patients planned for diagnostic endoscopy of the gastrointestinal tract or bariatric surgery at the University Hospital of Basel, the doctor's office MagenDarm Basel or the Department of Visceral Surgery, Hospital Lindenholz of Bern will be considered, contacted and informed about the study. Ample time for consideration and the opportunity to ask questions will be given. Written informed consent will be obtained according to pertinent regulations. No laboratory or diagnostic tests are necessary for inclusion of the patient. As the study does not involve any additional procedures for the patient, no compensation will be paid. Substudy (validation of diet questionnaire): Normal- and overweight people from the Department of Endocrinology will be asked to fill out a diet questionnaire (no inclusion or exclusion criteria).

3.3 Study procedures

Screening and inclusion: The study procedure is summarized below. The first patient is planned for September 2018 with a study duration of 2 years. Patients planned for endoscopies of the gastrointestinal tract or bariatric surgeries at the University Hospital Basel, the doctor's office MagenDarm Basel or the Hospital Lindenholz Bern will be screened for inclusion and exclusion criteria and informed about the study by the participating gastroenterologist, endocrinologist or visceral surgeon. Informed consent will be obtained at the latest on the day of the endoscopy or hospital admission for bariatric surgery.

Tissue sampling: Endoscopies or bariatric surgeries will be carried out as per clinical standard of care. Our collaborators are PD Dr. [name] at the Department of Gastroenterology and PD Dr. [name] at the Department of Visceral Surgery, University Hospital Basel, Dr. [name] and [name]. [name] at the doctor's office MagenDarm Basel and PD Dr. [name] at the Department of Visceral Surgery, Hospital Lindenholz Bern. The samples obtained from endoscopies comprise 10 to 12 biopsies per subject including two biopsies being frozen and later on analyzed for inflammatory markers (e.g. TNF α , IL6). The biopsies will be either collected in the Colon transversum in case of colonoscopy or in the stomach and duodenum in case of gastroscopy as we have seen in our mice study different subpopulations depending on the location. The tissue samples from the bariatric surgery are a 1cm piece of the jejunum that would normally be disposed. Additionally, four EDTA and one serum blood tube for the analysis of inflammatory cells and markers in the blood will be taken as well as a single stool sample.

Data: Medical data will be obtained from the patient's electronic health record. The work-up of the tissue specimen, the stool sample and the EDTA blood samples by flow cytometry will be carried out in the laboratory of PD Dr. [name]. Leftover tissue specimen will be snap frozen as well as the serum blood sample after centrifugation. We do not expect biases in our study.

Substudy (validation of diet questionnaire): For validation purposes, normal- and overweight people from the Department of Endocrinology will be asked to fill out a diet questionnaire called „Healthy Eating Index“ (modified after J. Russell) taking about 15 minutes.

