3 PROJECT POPULATION AND STUDY PROCEDURES

3.1 Project population, inclusion and exclusion criteria

Study population: To elucidate the role of intestinal immune cells in metabolic disease, human gut samples are necessary, which can be obtained from gut biopsies or surgical samples. As patients will undergo diagnostic endoscopy of the gastrointestinal tract or bariatric surgery for clinical reasons and the standard of care will not be changed by the study, there will be no additional interventions to patients by their participation in the study. Participants fulfilling the following inclusion criteria are eligible for the study:

For *colonic tissue samples*, 10 subjects per group referred to the Department of Gastroenterology at the University Hospital Basel or the doctor's office MagenDarm Basel, for a diagnostic colonoscopy on the basis of symptoms suggestive for irritable bowel syndrome or for a screening colonoscopy for colorectal cancer will be included:

- Obese weight non-smokers (BMI >32kg/m²), n=10
- Obese smokers (BMI >32kg/m², ≥1 pack cigarettes/d), n=10
- Normal weight non-smokers (BMI <27kg/m²), n=10
- Normal weight smokers (BMI <27kg/m², ≥1 pack cigarettes/d), n=10

For *tissue samples of the upper gastrointestinal tract and assessment of nutritional intervention*, 10 subjects per group referred to the Department of Visceral Surgery at the University Hospital Basel, the doctor's office MagenDarm Basel or the Department of Visceral Surgery, Hospital Lindenhof Bern, for bariatric surgery will be included. All bariatric patients receive a screening gastroscopy as standard of care prior to the surgery. Subjects willing to participate will contribute gastric and duodenal biopsies from the preoperative screening gastroscopy as well as an approximately 1cm long piece of the jejunum, which is usually disposed during bariatric surgery. As controls, 10 subjects referred to the Department of Gastroenterology at the University Hospital Basel or the doctor's office MagenDarm Basel, for an upper endoscopy on the basis of dyspeptic symptoms will be included as well.

- Obese non-smokers (BMI >35kg/m²) undergoing bariatric surgery, n=10
 - o a) Pre-diet: gastric and duodenal biopsies from the preoperative screening gastroscopy
 - o b) Post-diet: jejunal tissue specimen from bariatric surgery
- Normal weight non-smokers (BMI <27kg/m²), n=10

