4 STATISTICS AND METHODOLOGY

4.1. Statistical analysis plan

The study will entail samples collected from patients undergoing endoscopy of the gastrointestinal tract or bariatric surgery at the University Hospital Basel who sign an informed consent allowing to use their

tissue for research purposes. Samples sizes were calculated using G*Power, University Düsseldorf. The primary endpoint will be analyzed by Mann-Whitney U test assuming an alpha-error of 0.05 as limit of significance and a power of 0.95. Based on our preclinical mouse data experiments, we calculated an expected effect size of 2.4 (in terms of absolute numbers of intestinal macrophage subpopulation P1), leading to a necessary group size of 6 subjects per group. However, as we expect greater variance with human data compared to mice due to diet/ lifestyle, we suggest including 10 subjects per group as specified below, accounting for a total of study participants of 60:

Colonic tissue samples:

- Obese weight non-smokers (BMI >32kg/m²), n=10
- Obese smokers (BMI >32kg/m², ≥1 pack cigarettes/d), n=10
- Normal weight non-smokers (BMI <27kg/m²), n=10
- Normal weight smokers (BMI <27kg/m², ≥1 pack cigarettes/d), n=10

Tissue samples of the upper gastrointestinal tract and assessment of nutritional intervention:

- Obese non-smokers (BMI >35kg/m²) undergoing bariatric surgery, n=10
 - o a) Pre-diet: gastric and duodenal biopsies from the preoperative screening gastroscopy
 - o b) Post-diet: jejunal tissue specimen from bariatric surgery
- Normal weight non-smokers (BMI <27kg/m²), n=10

Descriptive statistics will be used for outcome measures. To compare groups (e.g. obese versus lean, smokers versus non-smokers) two-tailed non-parametric tests will be used (Mann-Whitney). A p-value <0.05 will be considered as statistically significant. These statistical analyses will be done with the help of GraphPadPrism.

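### Section 3.3 expects no bias and 4.1 specifies no adjusted analysis, yet in the upper GI comparison referral indication coincides with obesity, and in the colon age and sex may differ between groups

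*Combined protocol and SAP*

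**What the plan says.** Section 3.3 ends its paragraph on data with "We do not expect biases in our study". Section 2.3 describes a prospective observational study. Nowhere do the documents describe randomisation, matching, stratification or covariate adjustment.

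For group comparisons, section 4.1 says "two-tailed non-parametric tests will be used (Mann-Whitney", after descriptive statistics, with p<0.05 as the limit of significance. Sample size rests on mouse data: "we calculated an expected effect size of 2.4 (in terms of absolute numbers of intestinal macrophage subpopulation P1". This gives 6 per group, raised to 10.

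Section 3.1 sets the routes of entry:

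- **Upper GI, obese:** "All bariatric patients receive a screening gastroscopy as standard of care prior to the surgery". The pre-diet biopsies come from that gastroscopy.
- **Upper GI, lean controls:** 10 subjects referred "for an upper endoscopy on the basis of dyspeptic symptoms will be included as well".
- **Colon:** all four groups are drawn from the same two Basel sources and the same two indications (IBS-type symptoms or cancer screening).

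Section 7.2 lists date of birth and gender among the data collected. It does not list endoscopy indication or centre. Section 6.1 assumes that the results apply to the general population.

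**The concern.** The obese v lean comparisons in the colon and upper GI, and smokers v non-smokers in the colon, are primary endpoints (section 2.2). An unadjusted two-group test attributes any difference between groups to the factor that names them. That needs the groups to be alike in whatever else affects intestinal macrophages, and nothing in the design secures this for age, sex or reason for endoscopy.

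The two parts differ in kind. In the upper GI the overlap of indication and obesity is fixed by the eligibility criteria. In the colon, imbalance in age, sex or the mix of indications may or may not occur. Either could lead to a difference being reported as an obesity or smoking effect, or to a true effect being hidden. Section 4.1 expects more variation in humans from diet and lifestyle and answers it with a larger n, but a larger n does not remove a systematic difference between groups.

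**Working it through.** **1. The plan's sample size.** Inputs from 4.1: effect 2.4 SD, two-sided 5%, power 0.95, Mann-Whitney. With the normal-parent efficiency 3/π, effective n per group = 6 × 3/π = 5.73. Then df = 2 × 5.73 − 2 = 9.46, noncentrality = 2.4 × √(5.73/2) = 4.06, and power = 0.952. The stated 6 per group reproduces, so the arithmetic is not at fault. It takes the group difference to be the obesity effect alone.

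**2. Upper GI: can indication be separated?** Code obesity 1 for the 10 bariatric subjects and 0 for the 10 controls, and indication likewise. The two columns are identical. A design matrix with intercept, obesity and indication has rank 2, not 3, so no model on these 20 subjects can estimate both.

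**3. Upper GI: possible size.** The documents give no effect of indication, so the shifts are assumed. Setting: normal outcomes, exact two-sided Mann-Whitney, 10 v 10.

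Observed separation = obesity effect ± indication shift.

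| Obesity effect (SD) | Indication shift (SD) | Net separation (SD) | p<0.05 |
|---|---|---|---|
| 0 | 0 | 0 | 4% |
| 0 | 0.5 | 0.5 | 16% |
| 0 | 1.0 | 1.0 | 51% |
| 1.5 (assumed) | 0.5, opposing | 1.0 | about 51%, from 85% unshifted |
| 1.5 (assumed) | 1.0, opposing | 0.5 | 16%, from 85% unshifted |
| 2.4 (plan) | 0.5, opposing | 1.9 | 97%, from 99.8% unshifted |
| 2.4 (plan) | 1.0, opposing | 1.4 | 80%, from 99.8% unshifted |

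With no obesity effect, significant results run almost wholly in the direction of the shift (0.1% or fewer of studies the other way). If the shift comes from dyspeptic symptoms and 25% of bariatric patients share them, the 16% and 51% become 11% and 29%; if 50% share them, 7% and 15%. The documents do not give that share.

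**4. Colon: possible size.** Assumed: no obesity effect, age gap g between obese and lean, and age-outcome correlation 0.4. The spurious separation is 0.4 × g, that is 0.2 SD for g = 0.5 and 0.4 SD for g = 1.0. The adjusted analysis is a linear model on outcome ranks with obesity, smoking, age and sex, using all 40 subjects.

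| Age gap (SD) | Mann-Whitney, 10 v 10 | Mann-Whitney, 20 v 20 | Adjusted, 40 subjects |
|---|---|---|---|
| 0.5 | 6-7% | 9% | 5% |
| 1.0 | 12% | 22% | 5-6% |

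With no gap, or no link between age and outcome, the unadjusted rate stays at 4-5%. A sex split of 35% v 65% with a sex effect of 0.5 or 1.0 SD gives 8% or 13% unadjusted at 20 v 20, against 5% adjusted. Section 4.1 sizes groups at 10 and does not say whether cells are pooled, so both sizes are shown.

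**5. Cost of adjusting** (1 SD effect, 20 v 20). Power is 83-84% adjusted v 85% unadjusted if age and sex are balanced and irrelevant. It is about 75% v 85% if age differs by 1 SD but does not affect the outcome. It is 88% v 85% if age is balanced with correlation 0.4.

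**The case against.** Much can be said for the plan. It is openly observational, tissue must come from clinically indicated procedures, and both upper GI indications are disclosed. The exclusions for drugs, infection and inflammatory bowel disease, the crossing of obesity with smoking in the colon, the restriction to non-smokers in the upper GI, one colon segment and one laboratory are real controls. The sentence in 3.3 follows directly on the laboratory work-up and may concern measurement only. All of this stands, but none of it covers age, sex or indication, and the plan nowhere states the upper GI limitation.

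Four stronger readings are tempting, and the documents do not support them.

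- **That the colon comparison is biased.** All four groups share sources and indications. No age or sex gap, and no link to the outcome, is documented.
- **That age and sex are ignored altogether.** Section 7.2 sends collected numerical values to the analysis software, and section 2.2 plans correlations with eating habits. What is missing is a specified adjusted analysis.
- **That centre is confounded with obesity too.** Bariatric subjects may come from "MagenDarm Basel or the Department of Visceral Surgery, Hospital Lindenhof Bern, for bariatric surgery will be included", and the Bern hospital supplies no controls. But controls start from "As controls, 10 subjects referred to the Department of Gastroenterology at the University Hospital Basel" and also come from the Basel practice, so both Basel sources can supply both groups. Bern's share is not given, and 4.1 refers only to "bariatric surgery at the University Hospital Basel who sign an informed consent".
- **That the adjusted model should replace Mann-Whitney.** Without an obesity-by-smoking term it averages over smokers and non-smokers. If an assumed 1.5 SD obesity effect exists only in non-smokers, it has about 52% power, against about 85% for the 10 v 10 Mann-Whitney in non-smokers.

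**Conclusion.** The point holds in two parts of different strength. In the upper GI, the inability to separate obesity from referral indication follows from section 3.1 and needs no assumption. Only its size is assumed: 16% or 51% significant results without an obesity effect, for shifts of 0.5 or 1.0 SD. A shift that favours the hypothesis mimics it, and an opposing shift masks it. Masking would cost little at the plan's own 2.4 SD but much at 1.5 SD.

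In the colon it is a risk that depends wholly on an assumed imbalance and an assumed link to the outcome. At correlation 0.4 the excess over 5% is small at 10 v 10 for a 0.5 SD gap, and clear only for a 1.0 SD gap or pooled groups. Bias is not shown in either part. The change is still worth making: the no-bias statement cannot stand for group comparability, and the data for an age and sex adjustment are already to be collected.

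**What to change.** 1. **Sections 3.3 and 6.1.** Replace the no-bias sentence with a statement that, in the upper GI, obese v lean differences cannot be separated from referral indication (pre-bariatric v dyspepsia). Limit the upper GI conclusion and the general-population sentence in 6.1 accordingly.
2. **Section 4.1.** Keep Mann-Whitney as the main test. For the colon, pre-specify a sensitivity analysis: a rank-based linear model with obesity, smoking, age and sex. Report the obesity effect within non-smokers and within smokers (through an obesity-by-smoking term) as well as averaged. State that an obese v lean or smoker v non-smoker difference that does not persist after adjustment will not be attributed to obesity or smoking. Say how persistence is judged, preferably by the estimate and its interval, because significance alone can be lost through lower power.
3. **Section 7.2 and the CRF.** Record endoscopy indication and centre. Repeat the colon model with indication, and describe any imbalance in centre.

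**Cost.** SAP wording, two CRF items and a little more analysis; no extra subjects or samples. The adjusted analysis gives up some power in the cases shown in step 5 of the working, but it is supporting and the main test is unchanged. Effects within smokers or non-smokers will be less precise than the average. The software named in 4.1 must be able to fit the model, or another must be named.

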2.2 Primary and secondary endpoints

Primary endpoints: In our preclinical studies, we found that mice fed a high fat diet had a shift of intestinal macrophages towards inflammatory subpopulations, which precedes adipose tissue inflammation. We think that intestinal macrophages could also be involved in human metabolic disease. Therefore, our primary endpoint is to investigate:

- 1) the frequency & subpopulations of intestinal macrophages from the *colon* in obese versus lean subjects and smokers versus non-smokers,
- 2) the frequency & subpopulations of intestinal macrophages from the *upper gastrointestinal tract* in obese versus lean subjects,
- 3) the frequency & subpopulations of intestinal macrophages from the upper gastrointestinal tract in obese subjects *before and after a nutritional intervention*.

Secondary endpoint: Besides macrophages, also other intestinal immune cells could be implicated in metabolic disease. For example, one preclinical study found that adaptive immunity might be involved²². In case we do not find clear differences in frequency or subpopulations of intestinal macrophages, we will assess other intestinal immune cells (e.g. B-, T-lymphocytes), and enteroendocrine cells (e.g. L-cells) as a secondary endpoint in an explorative manner. Additionally, we aim to correlate our findings from the biopsy samples with inflammation markers and immune cells in the blood, with microbiota and immune cells in the stool and with the eating habits of the patients.

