7 QUALITY CONTROL AND DATA PROTECTION

7.1 Quality measures

For quality assurance, we will develop standard operating procedures for handling and analyses of tissues samples.

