7.2 Data recording and source data

Available medical data about date of birth, gender, race, weight, height, BMI, waist and hip circumference, blood pressure, heart rate, smoking status, alcohol consumption, diabetes (including date of diagnosis), other relevant diagnoses, diet and drugs within past month before samples collection, family history regarding diabetes, obesity, cardiovascular diseases, laboratory values for Hb, HbA1c, leucocytes and their differentiation, lipids, CRP, creatinine, AST, ALT, AP and total bilirubin will be collected from hospital records and documented in a coded manner in paper Case Report Forms (CRF). Numerical values will be later transferred into GraphPad prism for statistical analysis. The original source data file will be archived. Changes of the data will be saved as separate files with accompanying information why values had to be modified. Upon the participant's permission, medical information may be given to his or her personal physician or other appropriate medical personnel responsible for her or his welfare.

Data retrieved from biological material regarding intestinal macrophages will be stored in a coded manner in GraphPad prism files upon analysis.

Participants will be asked whether the data obtained during this research project may be used for subsequent projects or secondary analyses.

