7.3 Confidentiality and coding

Medical data obtained for this study is confidential and is only accessible to authorized personnel who require the data to fulfil their duties within the scope of the research project. Disclosure to third parties

other than those noted below is prohibited. Confidentiality of the subjects will be maintained by assigning subjects an ID number, keeping identifiers separate from the data and storing data in a locked file in the department of Endocrinology, Diabetes and Metabolism. The principle investigator and the co-investigators will have access to the encryption list.

Biological material in this project is not identified by participant name, but by a unique ID number. Biological material is appropriately stored in a restricted area only accessible to authorized personnel.

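### The plan expects no bias, but nothing masks the flow-cytometry analysis behind the primary endpoint to group or fixes it before groups are linked

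*Combined protocol and SAP*

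**What the plan says.** Section 2.2 defines the primary endpoints as "the frequency & subpopulations of intestinal macrophages from the" colon (obese v lean, smokers v non-smokers) and the upper gut (obese v lean, and obese before v after diet). Section 3.3 places the measurement in a single laboratory: "The work-up of the tissue specimen, the stool sample and the EDTA blood samples by flow cytometry". The same section says "We do not expect biases in our study", with no reason and no safeguard attached.

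Four other statements bear on who could know the group:

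- Section 7.3, labelling: "Biological material in this project is not identified by participant name, but by a unique ID number".
- Section 7.3, access to the code: "The principle investigator and the co-investigators will have access to the encryption list".
- Section 7.2, storage: "Data retrieved from biological material regarding intestinal macrophages will be stored in a coded manner in GraphPad prism files upon analysis". The same section puts BMI and smoking status in the coded paper case report form (CRF).
- Section 7.1, procedures: "we will develop standard operating procedures for handling and analyses of tissues samples". Their content is not given.

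No section mentions masking of the cytometry analysis, a gating strategy, or a lock of the values before group data are joined to them.

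**The concern.** Cell subpopulations in flow cytometry are commonly separated by boundaries (gates) that an analyst draws. This is general knowledge of the method; the documents do not describe it. If the analyst knows whether a sample comes from an obese or lean subject, or from a smoker, small choices can move in step with group. Section 2.1 states a direction for metabolic disease, a pro-inflammatory shift, so an analyst who knew a subject was obese would also know which result was hoped for.

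A shift introduced at measurement looks the same to a Mann-Whitney test as a biological one. Larger groups do not help, because they detect the spurious difference more reliably. The protection has to come from how the samples are read, and the plan describes none beyond coding.

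**Working it through.** **1. The plan's own figure.** Section 4.1 gives effect size 2.4, alpha 0.05, power 0.95, a Mann-Whitney test (two-tailed) and 6 per group. For normal data, use the noncentral t with asymptotic relative efficiency 3/π:

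- effective n = 6 × 3/π = 5.73 per group
- df = 2 × 5.73 − 2 = 9.46
- noncentrality = 2.4 × √(5.73/2) = 4.06
- power = 0.952

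The stated 6 per group reproduces. Nothing below changes it, or the planned 10 per group and 60 in total.

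**2. Does any safeguard amount to masking?**

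| Safeguard | What it does | What it leaves open |
|---|---|---|
| ID instead of name (7.3) | Protects identity | Investigators can open the list; not stated whether the cytometry analyst is one of them |
| Coded storage (7.2) | Governs how macrophage results are filed | Who knew the group when the values were produced |
| Coded CRF (7.2) | Removes the name | BMI and smoking status sit beside the ID, so group can be read without the list |
| Procedures to come (7.1) | Could hold a gating template | Not yet written; masking not mentioned |

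None of the four, alone or together, keeps the analyst from knowing the group.

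**3. Which comparisons can be masked?**

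- Colon: all biopsies come from the transverse colon (3.3), so the tissue does not reveal the group.
- Upper gut, obese v lean: gastric and duodenal biopsies in both groups. Referral route would reveal the group, because obese subjects are referred for bariatric surgery and controls for dyspeptic symptoms (3.1).
- Pre- v post-diet: gastric and duodenal biopsies before, a jejunal piece after (3.1). Tissue type reveals the time point, so masking is not possible.

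**4. Illustration of size.** The documents give no figure for a measurement shift, so the shifts are assumptions. Setting: two independent groups, normal data, no true difference, a constant shift between groups, exact two-sided Mann-Whitney at 0.05, 20,000 simulations per cell.

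| Assumed shift (SD) | False positives, 10 v 10 | False positives, 20 v 20 |
|---|---|---|
| 0 | 4.3% | 5.0% |
| 0.25 | 6.9% | 11.5% |
| 0.5 | 16.3% | 32.4% |
| 1.0 | 52.1% | 84.9% |

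The 20 v 20 column applies only if the colon groups are pooled over the other factor, which section 4.1 does not specify. Against the planning effect of 2.4, a shift of 0.25 SD is 0.25/2.4 = 10% and 0.5 SD is 0.5/2.4 = 21%. The table does not apply to the pre- versus post-diet comparison, which is within subject.

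**The case against.** The strongest reply is that the concern is built on silence. The documents never mention gates, an operator or gate revision; fixed or automated gating is neither stated nor excluded. The procedures promised in section 7.1 are the normal place for a gating template. Section 7.2 also archives the original source file and keeps changes as separate files with reasons, although it is not clear that this reaches the cytometry files. The sizes in the illustration are assumed, and any assumed bias inflates the false-positive rate.

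Most of this stands, and it limits what can be claimed. A reader might infer any of the following, and the documents support none of them:

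- *Gates will be redrawn sample by sample with the group known.* No section says so. The text only fails to prevent it.
- *Smokers, like obese subjects, are expected to look more inflammatory.* Section 2.1 gives a direction for metabolic disease. For particulate exposure it says only that macrophages could be altered.
- *Withholding the encryption list would be enough.* It would not, because the coded CRF carries BMI and smoking status.
- *Every primary comparison is exposed in the same way and can be repaired in the same way.* The pre- versus post-diet comparison cannot be masked.

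The reply does not supply a reason for the no-bias sentence. Coding for confidentiality is not masking, and procedures not yet written cannot be relied on as a safeguard.

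**Conclusion.** The point holds in a limited form. The primary endpoint is a laboratory readout, the plan dismisses bias without argument, and nothing in it masks the analyst or fixes the analysis before linkage. If the gates are set by someone who knows the group, that knowledge could shift the obese-versus-lean comparisons, where a direction is stated, and the smoker comparison, where none is.

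The size cannot be derived from the documents. With assumed shifts of 0.25 to 0.5 SD and no true difference, the false-positive rate at 10 v 10 goes from about 4% to about 7% to 16%. This rests on normal data, a constant shift and independent groups. It shows what a modest shift would do and does not estimate a bias that is present. No planned sample size is affected.

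**What to change.** In section 3.3, and in the procedures of section 7.1, state that:

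1. a gating strategy is fixed for each tissue site before group data are linked (one per site, because section 3.3 reports that subpopulations differed by location in mice);
2. existing laboratory personnel analyse samples under coded IDs, without access to the encryption list or to information that reveals group (BMI, smoking status, referral source);
3. the gated values are locked before linkage;
4. the pre- versus post-diet comparison cannot be masked, because tissue type reveals the time point.

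Replace the sentence that no bias is expected with this text.

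The cost is small: the analyst's access is restricted until lock. The coded IDs already exist, participants undergo nothing more, and 10 per group and 60 in total stand. The documents do not describe laboratory staffing, so the sponsor should confirm that someone without access to the list and the CRF can do the analysis.
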